11.4.3.1 Adverse events

Adverse event incidence tables will be presented by system organ class (sorted by internationally agreed order), high-level group term, high-level term, and preferred term sorted in alphabetical order for each treatment group, the number (n) and percentage (%) of patients experiencing an AE. Multiple occurrences of the same event in the same patient will be counted only once in the tables within a treatment period. The denominator for computation of percentages is the safety population within each treatment group.

Adverse events will be coded according to the Medical Dictionary for Regulatory Activities. The AEs will be classified into predefined standard categories according to chronological criteria:

- Pretreatment AEs: AEs that occurred or worsened during the pretreatment period;
- Treatment-emergent AEs: AEs that occurred or worsened during the on-treatment period;
- Post-treatment AEs: AEs that occurred or worsened during the post-treatment period.

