
DURATION OF STUDY PERIOD (PER PATIENT)
	
Part 1
 
Total duration: up to approximately 50 weeks (or 68 weeks for Japanese patients), in total. Patients will receive either placebo or GZ/SAR402671. Dosing will be for minimum 8 weeks per cohort and maximum of 36 weeks (or 52 weeks for Japanese patients), for Cohort 1. After 4 weeks of dosing, an internal blinded data review will occur, ensuring no safety/tolerability issues, the next cohort of patients will be dosed.
 
Part 2
 
Total duration: up to approximately 208 weeks (4 years), excluding Periods 1 and 4.
 
There are 4 study periods:
 
Period 1: up to 60 days of screening period;
 
Period 2: up to 52 weeks of blinded treatment period;
 
Period 3: up to 156 weeks LTFU period when all patients will be on active drug; and,

	
Period 4: 8-week post-treatment observation period/end of study visit.
 
Therefore, maximum duration for a patient will be approximately 224 weeks.
 
At the end of Period 2, all patients will be evaluated for eligibility to transition to the LTFU period (Period 3) where they will continue to receive appropriate monitoring and will receive GZ/SAR402671. It is important to note that patients will not be informed of when the switch will occur, nor will the person(s) performing any of the evaluations.

--	-------------------------------------------------------------------------------------------------------------------------------------------------------------------------------------------------------------------------------------------------------------------------------------------------------------------------------------------------------------------------------------------------------------------------------------------------------------------------------------------------------------------------------------------------------

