5 STUDY OBJECTIVES

5.1 PART 1: DOSE ESCALATION PHASE

5.1.1 Primary objective

To determine the safety and tolerability of 4, 8, and 15 mg of GZ/SAR402671, as compared to placebo, when administered orally daily for 4 weeks in early-stage PD patients carrying a GBA mutation or other prespecified sequence variants (from now on both mutation types are referred to as 'GBA mutation'). This will allow selection of the dose for the second part of this study (this does not apply to Japanese patients).

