6 STUDY DESIGN

6.1 DESCRIPTION OF THE STUDY

This is a two-part, multicenter, multiple-country, randomized, double-blinded, placebo-controlled study in early-stage PD patients carrying a GBA mutation. The study will be divided into 2 consecutive parts. Part 1 will be a randomized, double-blinded, placebo-controlled dose escalation study, utilizing a sequential cohort design. Part 1 will allow selection of the dose of GZ/SAR402671 for Part 2, a randomized, double-blind, placebo-controlled, 2-arm study of the efficacy and safety of GZ/SAR402671. Part 1 will be conducted only in selected sites (approximately 20 sites [including 4 Japanese sites]); Part 2 will be conducted at multiple sites (approximately 50). Part 2 will start after the appropriate dose for Part 2 is selected in Part 1.

In Part 1, during the screening/baseline period, from Day -60 to Day -1, patients will provide informed consent and undergo screening assessments to determine trial eligibility and undergo baseline measurements. If all eligibility criteria are met, patients will enter the trial. Part 1 will determine the safety and tolerability of GZ/SAR402671 at 4, 8, and 15 mg in early-stage PD patients carrying a GBA mutation by using a dose escalation scheme (4 weeks to assess safety and tolerability of dose and a minimum of an additional 4 weeks to further assess safety and tolerability and any potential changes in other exploratory endpoints in each dose cohort). There will be 3 sequential cohorts that will be placebo-controlled:

- Cohort 1: 4 patients on GZ/SAR402671 4 mg and 1 patient on placebo.
- Cohort 2: 4 patients on GZ/SAR402671 8 mg and 1 patient on placebo.
- Cohort 3: 4 patients on GZ/SAR402671 15 mg and 1 patient on placebo.

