6.2 DURATION OF STUDY PARTICIPATION

6.2.1 Duration of study participation for each patient

The maximum study duration per patient will be approximately 224 weeks (4.3 years, patients from Part 2 only) to 272 weeks (5.5 years, patients from Part 1 enrolling in Part 2), or to 288 weeks for Japanese patients (5.9 years, Japanese patients from Part 1 enrolling in Part 2).

Part 1: Dose escalation phase

The maximum study duration per patient will be approximately 50 weeks (or 66 weeks for Japanese patients), inclusive of the screening period. Three sequential cohorts are planned. Patients will receive either placebo or GZ/SAR402671 (4 mg, 8 mg, or 15 mg) for a minimum 8 weeks per cohort (and maximum of 36 weeks [or 52 weeks for Japanese patients], for Cohort 1).

Safety/tolerability data will be analyzed at the end of 4 weeks of treatment at each cohort before proceeding to the next cohort.

Part 2: Treatment phase

The total study treatment duration (Periods 2 and 3) is approximately 208 weeks (4 years).

The study comprises 4 main periods:

- Period 1: the up to 60-day screening period.
- Period 2: the 52-week double-blinded, randomized treatment period.
- Period 3: the 156-week LTFU period during which eligible patients will all receive GZ/SAR402671.
- Period 4: the 8-week post-treatment observation period with end of study visit.

Therefore, maximum duration for a patient will be approximately 224 weeks.

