10.1.1.8 Visit 8: Week 8 (± 3 days)

The following assessments will be performed as listed in the study flow chart, [Section 1.3.1](#), which should be done in the following order:

- Whenever possible, the following scales and questionnaires should be done prior to clinical interaction with the Investigator:
 - BDI-II ([Appendix L](#))
 - PGIC ([Appendix N](#))
 - PDQ-39 ([Appendix O](#))
 - EQ-5D ([Appendix P](#))
 - HRPQ ([Appendix R](#))
 - MDS-UPDRS, including H&Y ([Appendix F](#))
 - PD-CRS ([Appendix G](#))
- Other questionnaires and scales
 - MoCA ([Appendix I](#))
 - Oral SDMT ([Appendix J](#))
 - TMT-A; TMT-B ([Appendix K](#))
 - CGI ([Appendix M](#))
- Review of concomitant medications
- Physical examination
- General neurological examination

- Vital signs: systolic and diastolic blood pressure (mm Hg), heart rate (bpm), respiratory rate (breaths/minute), and temperature (°C)
- Urine pregnancy test (for WOCBP)
- Review of current medical conditions, with AE/SAE reporting (if any)
- Blood sampling for PK analyses (1 hour before dosing)
- Dispense IMP

Remind patient to return to the clinic for next visit, bring their diary and any remaining capsules.

Remind patient to not take the dose at home on the clinic visiting day, the IMP will be taken at clinic.

*10.1.1.8.1 Visits 8.1 – 8.7 (Visits 8.8-8.11 for Japanese patients only): Weeks 12-36
(Weeks 40-52 for Japanese patients only) (±3 days)*

This visit must be repeated for all ongoing patients every 4 weeks until all patients from Cohort 3 complete Part 1. A maximum of 36 weeks of treatment will be allowed (applicable to patients in Cohort 1), ie, up to 7 additional visits (8.1-8.7) may be required. In Japan ([Appendix T](#)), a maximum of 52 weeks of treatment will be allowed (applicable to patients in Cohort 1), ie, up to 11 additional visits (8.1-8.11) may be required.

The following assessments will be performed as listed in the study flow chart, [Section 1.3.1](#), which should be done in the following order:

- MDS-UPDRS, including H&Y ([Appendix F](#))
- BDI-II ([Appendix L](#))
- Review of concomitant medications
- Physical examination
- General neurological examination
- Visual acuity check, slit lamp examination and fundoscopy without pupil dilation only at Weeks 12 and 28 (Week 36 for Japanese patients), if applicable
- Full ophthalmology examination and photography at Week 36 (or Week 52 for Japanese patients), if applicable

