11.4.3 Analyses of safety data

Safety data will be described separately for Part 1 and Part 2 of the study, and separately for Japanese and non-Japanese patients.

Safety and tolerability in the Japanese patients from Part 1 will be compared to the non-Japanese patients.

All safety analyses will be performed on the Part 1 safety population and Part 2 safety population respectively. The summary of safety results will be presented by treatment group actually received.

The baseline value is defined generally as the last available value before randomization, within each part of the study.

For all safety data, the observation period will be divided into 3 segments within each part of the study:

- The **pretreatment period** is defined as the time between the date of the informed consent and the first administration of double-blind IMP.
- The **on-treatment period** is defined as the period from the time of first IMP administration up to 6 weeks after the last administration of the IMP.
- The **post-treatment period** starts on the day after the end of the on-treatment period.

The following definitions will be applied to laboratory parameters, vital signs, and ECGs.

- The potentially clinically significant abnormality (PCSA) values are defined as abnormal values considered medically important by the Sponsor according to predefined criteria/thresholds based on literature review and defined by the Sponsor for clinical laboratory tests, vital signs, and ECGs.
- The PCSA criteria will determine which patients had at least 1 PCSA during the on-treatment period, taking into account all evaluations performed during the on-treatment period, including unscheduled or repeated evaluations. The number of all such patients will be the numerator for the on-treatment PCSA percentage.

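### Part 1 AE and PCSA percentages ignore that lower-dose cohorts are followed on treatment longer by design, which biases by-dose safety tables toward fewer events at 15 mg

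*Protocol*

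**What the plan says.** Part 1 has three sequential dose cohorts. Protocol section 6.1 describes the first as "Cohort 1: 4 patients on GZ/SAR402671 4 mg and 1 patient on placebo", followed by 8 mg and then 15 mg with the same numbers. The clinical trial summary sets the dosing time: "Dosing will be for minimum 8 weeks per cohort and maximum of 36 weeks (or 52 weeks for Japanese patients), for Cohort 1". Section 6.2.1 repeats these limits. Section 10.1.1.8.1 explains why the early cohorts stay on drug longer: "This visit must be repeated for all ongoing patients every 4 weeks until all patients from Cohort 3 complete Part 1".

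Section 11.4.3 fixes the safety window. The time that counts as on treatment "is defined as the period from the time of first IMP administration up to 6 weeks after the last administration of the IMP". Section 11.4.3.1 counts a patient once per event and then states: "The denominator for computation of percentages is the safety population within each treatment group". For PCSAs, sections 11.4.3 and 11.4.3.2 count any patient with at least one abnormal value at any on-treatment evaluation, including unscheduled ones. Section 11.4.3 also commits to a comparison: "Safety and tolerability in the Japanese patients from Part 1 will be compared to the non-Japanese patients".

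The Part 1 primary objective (5.1.1) is safety and tolerability of each dose against placebo "when administered orally daily for 4 weeks in early-stage PD patients carrying a GBA mutation". Section 9.1.1 makes safety of each dose cohort the Part 1 primary endpoint.

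**The concern.** A crude percentage compares groups fairly only if they are observed for similar lengths of time. Here the sequential design ties observation time to dose: the lowest dose is followed longest and the highest dose shortest. A patient followed longer has more time to have a first event and more tests at which an abnormal value can appear. If the true event rate were the same at every dose, the tables would still be expected to show fewer affected patients at 15 mg.

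What is at stake is the reported Part 1 safety profile by dose, any single dose set against placebo patients drawn from all cohorts, and the comparison of Japanese with non-Japanese patients. The protocol's own objective is framed over 4 weeks, a period every cohort shares, but the analysis section does not use it.

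**Working it through.** **Inputs.** Dosing is at least 8 weeks in any cohort and at most 36 weeks (52 in Japan) in Cohort 1 (summary; 6.2.1). The on-treatment tail is 6 weeks (11.4.3). Each cohort must complete 4 weeks and be reviewed before the next starts (6.1). Visits come from the Part 1 flow chart (1.3.1). Event and abnormality rates are not in the protocol and are assumed, with ranges.

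**Step 1: reproduce the plan's duration.** Screening + dosing + 6 weeks = 60/7 + 36 + 6 = 50.6 weeks, against about 50 stated in 6.2.1. For Japan, 60/7 + 52 + 6 = 66.6, against 66 in 6.2.1. The summary gives 68 for Japan; the two should be reconciled, but nothing below depends on it.

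**Step 2: on-treatment windows (dosing + 6 weeks).**
- Fastest schedule, with no enrolment or review delay: Cohort 1 doses for 4 + 4 + 8 = 16 weeks, Cohort 2 for 4 + 8 = 12, Cohort 3 for 8. Windows are 22, 18 and 14 weeks; 22/14 = 1.6.
- Cap against floor: 36 + 6 = 42 versus 8 + 6 = 14 weeks, ratio 3.0. In Japan, 52 + 6 = 58 versus 14, ratio 4.1.

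**Step 3: expected crude incidence with no dose effect.** Incidence = 1 − exp(−h × w/52), where h is first events per patient-year (assumed 1, range 0.5 to 2) and w is the window in weeks.

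| Case | Window, 4 mg v 15 mg | h = 0.5 | h = 1 | h = 2 |
|---|---|---|---|---|
| Fastest schedule | 22 v 14 | 19.1% v 12.6% | 34.5% v 23.6% | 57.1% v 41.6% |
| Cap v floor | 42 v 14 | 33.2% v 12.6% | 55.4% v 23.6% | 80.1% v 41.6% |
| Cap v floor, Japan | 58 v 14 | 42.7% v 12.6% | 67.2% v 23.6% | 89.3% v 41.6% |

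With 4 active patients per dose and h = 1, this is 4 × 0.345 = 1.4 versus 4 × 0.236 = 0.9 affected patients on the fastest schedule, and 4 × 0.554 = 2.2 versus 0.9 at the extreme.

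**Step 4: number of tests.** Scheduled post-baseline laboratory panels at cap versus floor: Weeks 2 and 4, Visits 8.1 to 8.7 and Visit 9 = 10, against Weeks 2 and 4 and Visit 9 = 3. On the fastest schedule Cohort 1 has Weeks 2, 4, 12, 16 and Visit 9 = 5, against 3. If each panel independently has an assumed 2% chance of a PCSA, the chance of at least one is 1 − 0.98^10 = 18% versus 1 − 0.98^3 = 6% at the extreme, and 1 − 0.98^5 = 10% versus 6% on the fastest schedule. At an assumed 5% per panel the extreme is 40% versus 14%.

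**Step 5: the other comparisons.**
- Placebo: the active-to-placebo ratio is the same in each cohort, so all doses pooled against all placebo patients is balanced for time. One dose against pooled placebo is not. On the fastest schedule with h = 1, pooled placebo is expected to show (34.5 + 29.3 + 23.6)/3 = 29.1% against 23.6% at 15 mg.
- Japanese versus non-Japanese: only the Cohort 1 caps differ (52 versus 36 weeks); the 8-week minimum is common. At both caps the 4 mg windows are 58 versus 42 weeks, giving 67.2% versus 55.4% at h = 1.

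**Step 6: with a common window.** Over the first 4 weeks the same formula gives 3.8%, 7.4% and 14.3% for h = 0.5, 1 and 2, identical at every dose.

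**The case against.** **The dose decision does not rest on these tables.** A reader might infer that the tables could tilt the choice of the Part 2 dose toward 15 mg. The documents do not support that. The review before each escalation uses 4 weeks of data in every cohort (6.1, 6.2.1, 8.3.1). Its triggers are individual events, namely a related SAE or Grade 3 or higher AE, or the same such event in two patients of a cohort. The selection rule in 6.1 asks for the highest dose found safe and well tolerated, which is not a ranking of percentages between doses. Section 5.1.1 excludes Japanese patients from dose selection. This objection stands.

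**42 versus 14 weeks is a cap against a floor.** It should not be read as the expected gap. Early enrollees in Cohort 3 can also exceed 8 weeks. This stands, but the sequential design still leaves a gap of about 22 versus 14 weeks at its fastest for patients who stay on drug, and delay in escalation lengthens the earlier cohorts' exposure.

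**Groups are tiny and Part 1 is exploratory.** There are 4 active patients per dose (3 in Japan), so the bias is in expectation and a given table need not show it. It also shrinks if events cluster in the first weeks. Both points stand.

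**Part of this is already covered.** Exposure is summarised (11.4.1), and laboratory and vital-sign statistics are given by visit (11.4.3.2), which is like for like at shared visits. That does not reach TEAE incidence, PCSA incidence or worst values.

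**It belongs in the SAP.** A SAP may add tables. But the protocol itself fixes the window, the counting rule and the denominator, so this is a stated rule and not missing detail.

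**By-dose tables are partly inferred.** Section 11.3.2 names treatment received only as active or placebo. The by-dose reading rests on 5.1.1 and 9.1.1, which frame Part 1 safety by dose.

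**Conclusion.** The concern holds as a reporting fault. Part 1 TEAE and PCSA percentages by dose are biased in expectation toward fewer affected patients at the highest dose, and they answer a different question from the 4-week primary objective. With equal constant hazard of 1 first event per patient-year (assumed), the distortion runs from about 34% versus 24% on the fastest schedule to 55% versus 24% at the protocol's limits outside Japan. Scheduled laboratory panels run from 5 versus 3 to 10 versus 3. The Japanese versus non-Japanese comparison is affected to a lesser degree. These figures rest on patients staying on drug, a constant hazard, and Cohort 3 at its 8-week minimum.

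The escalation review is not affected, and nothing in the protocol shows that the Part 2 dose choice is.

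**What to change.** In section 11.4.3, state that Part 1 comparisons of TEAEs and PCSAs by dose, versus placebo, and Japanese versus non-Japanese are made over first dose to Week 4, with first dose to Week 8 as support. For laboratory PCSAs the Week 8 window adds no scheduled panel, since none is planned at that visit; it adds AE time and vital signs.

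Keep the patient counts over the full on-treatment period as descriptive tables. Show them with patient-time, give exposure-adjusted rates as a supplement, and state that they are not used to compare doses. Replacing the counts with rates alone would go too far: rates from 3 or 4 patients lean on a constant hazard, and late lens opacities, an AESI under 10.4.1.3, would become harder to see.

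The cost is a few sentences in 11.4.3 and 11.4.3.1 and one more set of tables. No new data are needed.

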Visit number	9.1 (for Japanese patients only)	10	10.1 (for Japanese patients only)	11	11.1 (for Japanese patients only)	12	12.1 (for Japanese patients only)	13	13.1 (for Japanese patients only)	14	14.1 (for Japanese patients only)	15	16
MDS-UPDRS (including H&Y)		X		X		X		X		X		X	X
PD-CRS		X		X		X		X		X		X	
MoCA		X		X		X		X		X		X	
SDMT (oral)		X		X		X		X		X		X	
TMT-A; TMT-B		X		X		X		X		X		X	
BDI-II		X		X		X		X		X		X	X
PDQ-39		X		X		X		X		X		X	
EQ-5D		X		X		X		X		X		X	
FES		X		X		X		X		X		X	
HRPQ		X		X		X		X		X		X	

Abbreviations: AE, adverse event; BDI-II: Beck Depression Inventory, second edition; CGI: Clinical Global Impression; DAT: dopamine transporters; DAT scan, ioflupane I-123 injection DaTSCAN; ECG: electrocardiogram; EQ-5D: EuroQol Five Dimensions questionnaire; FES: Falls Efficacy Scale; GL-1: glucosylceramide; H&Y: Hoehn and Yahr; HRPQ: Health-Related Productivity questionnaire; IMP, investigational medicinal product; lyso-GL-1: glucosylsphingosine; MDS-UPDRS: Movement Disorder Society-Unified Parkinson's Disease Rating Scale; MoCA: Montreal Cognitive Assessment; PD: Parkinson's disease; PD-CRS: Parkinson's Disease-Cognitive Rating Scale; PDQ-39: Parkinson's Disease Questionnaire – 39; qd, daily; SDMT: Symbol Digit Modalities Test; TMT-A: Trail-Making Test A; TMT-B: Trail Making Test B; WOCBP: women of childbearing potential.

- a* This is the study completion visit, and it should be done 8 weeks after last IMP dose; this visit also applies to early withdrawal or treatment discontinuation, if applicable. This does not apply to patients who will transition to a long-term study with GZ/SAR402671 (last visit will be week 208).
- b* Retrieve patient diary. For patients transitioning to a long-term study with GZ/SAR402671 the patient diary will be retrieved at week 208.
- c* Plasma biomarkers, including plasma GL-1 and lyso-GL-1.
- d* After 52 weeks, the patient is required to have a full ophthalmological examination at Weeks 104, 156, 208, and early withdrawal or treatment discontinuation, if applicable. Visual acuity check, slit lamp examination and funduscopy without pupil dilation are only required at Weeks 78, 130, 182, and 216 (at the 8-week follow-up [Period 4] visit). Pupil dilation/full evaluation can be performed at any time if deemed medically necessary.

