11.4.3.2 Laboratory data and vital signs

The summary statistics (including mean, standard deviation, median, Q1, Q3, minimum, and maximum) of all laboratory variables and all vital sign parameters (raw data and changes from baseline) will be calculated for each visit, last and worst value assessed during the treatment period, and presented by treatment group. For selected parameters, mean changes from baseline with the corresponding standard error will be plotted over time (at same time points) in each treatment group.

The incidence of PCSAs at any time during the TEAE period (on-treatment PCSAs) will be summarized by treatment group whatever the baseline level and/or according to the following baseline categories:

- Normal/missing.
- Abnormal according to PCSA criterion or criteria.

For laboratory parameters for which PCSA criterion is not defined, similar table(s) using the normal range could be provided.

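### Post-treatment adverse event percentages are divided by the whole safety population, including patients who have no post-treatment follow-up

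*Protocol*

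**What the plan says.** Section 11.4.3 cuts safety follow-up into segments: "For all safety data, the observation period will be divided into 3 segments within each part of the study". They are pretreatment, on-treatment and post-treatment. The second of these "is defined as the period from the time of first IMP administration up to 6 weeks after the last administration of the IMP", and the third begins the next day.

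Section 11.4.3.1 classifies adverse events by the same segments. The last class reads "Post-treatment AEs: AEs that occurred or worsened during the post-treatment period". For every incidence table it gives one denominator, with no exception by segment: "The denominator for computation of percentages is the safety population within each treatment group". Section 11.3.2 defines the Part 2 safety population as randomized Part 2 patients with at least one dose, leaving out those re-randomized from Part 1.

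Two other places decide who can have post-treatment time:

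- Section 11.5.2 plans a first-step analysis once the Week 52 data of Part 2 are complete, using all safety data available by then, and a second step at the end of the study.
- Section 1.3.3, footnote a, describes the visit 8 weeks after last dose and then says: "This does not apply to patients who will transition to a long-term study with GZ/SAR402671 (last visit will be week 208". Section 10.1.2.10 confirms that Visit 15 at Week 208, where the last dose is given, is the final visit for these patients.

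**The concern.** A percentage is read as a risk, and a reader assumes that the people in the denominator could have had the event. That holds for treatment-emergent events, because everyone in the safety population has on-treatment time. It holds for pretreatment events too. It does not hold for post-treatment events: by design, many treated patients may not yet have reached that segment, or may never reach it within this study.

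What is at stake is how post-treatment tables are read. Section 10.1.2.11 schedules the BDI-II at Visit 16. Section 9.4.5.4 requires a score of 20 or more, or certain answers to question 9, to lead to referral and to be recorded as an adverse event. Such an event, if dated to Visit 16, would normally be post-treatment. Under the stated rule it would be divided by a number that includes patients who never had that visit. A rate that looks reassuringly low could simply reflect how few patients were followed.

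**Working it through.** The protocol states no adverse event percentage and no count of patients with post-treatment follow-up, so there is no figure of its own to reproduce. The check is to see who can contribute post-treatment time and then to derive the size of the effect.

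**Who has post-treatment time**

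1. *First step.* The on-treatment period lasts until 6 weeks after the last dose. A patient still taking study drug in Period 3 when the data are cut has not left it, so post-treatment time is zero. So is that of anyone whose last dose was less than 6 weeks before the cut. Time beyond 6 weeks belongs to patients who stopped treatment early or did not enter Period 3, and were followed long enough.
2. *Second step, patients moving to the long-term study.* Last dose and last visit are both at Week 208. The on-treatment period would run to Week 208 + 6 = Week 214, after the patient has left this study. Post-treatment time in this study is zero.
3. *Second step, patients who attend Visit 16.* The visit is nominally 8 weeks after last dose, so post-treatment time is about 8 − 6 = 2 weeks. These patients are truly at risk in the segment.

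**Size of the effect**

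Let N be the safety population in one treatment group, m the number of those with post-treatment follow-up, and r the proportion of the m with the event.

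- Events = r × m
- Percentage under the stated rule = r × m / N
- Percentage among those observed = r
- Ratio of the first percentage to the second = m / N, the share with post-treatment follow-up

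Illustration with N = 108 per group (Section 11.1, taking all randomized patients as treated) and r = 10%. The shares are assumptions, since the protocol gives none.

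| Assumed share m/N | m (of 108) | Shown under the rule |
|---|---|---|
| 10% | about 11 | 10% × 0.10 = 1% |
| 20% | about 22 | 10% × 0.20 = 2% |
| 30% | about 32 | 10% × 0.30 = 3% |
| 50% | 54 | 10% × 0.50 = 5% |
| 90% | about 97 | 10% × 0.90 = 9% |

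The effect is large when few patients have such follow-up, which is the situation to expect at the first step, and small when nearly all have it.

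**The case against.** The strongest reply is that a percentage of all treated patients is an openly defined crude incidence, printed beside its count, and that table details of this kind usually belong in the SAP. The first part stands: the percentage is a valid quantity, and to say that it misstates incidence would go too far. It understates risk among the patients observed. The second part carries less weight here, because the protocol does not leave the denominator open. It fixes one, with no exception for a segment that it defines itself.

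It is also fair to say that events in the first 6 weeks after the last dose already count as treatment-emergent, and that for a patient ending at Visit 16 the post-treatment segment is only about 2 weeks. The point therefore concerns late events only, not everything that follows stopping.

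Two wider readings are tempting but are not supported:

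- *Period 3 tables.* A reader might infer that Period 3 percentages also use the whole safety population, since Section 11.4.3.1 says "Multiple occurrences of the same event in the same patient will be counted only once in the tables within a treatment period". That sentence governs repeat events in one patient and creates no Period 3 table. Period 3 is not one of the three safety segments, and Section 11.5.2 leaves safety analyses up to Week 208 to the SAP.
- *Laboratory and vital-sign tables.* A reader might infer that Section 11.4.3.2 loses patients whose baseline is abnormal without meeting the criterion for a potentially clinically significant abnormality. The section allows a summary regardless of baseline, which covers everyone. Set against the other group, "Abnormal according to PCSA criterion or criteria", the word normal most naturally means not meeting that criterion, so the two groups are exhaustive.

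**Conclusion.** The point holds, at minor severity, for post-treatment adverse event tables only. Under the rule as written, their percentages are too low as a measure of risk among patients observed in that period, by a factor equal to the share with post-treatment follow-up. The direction follows from the protocol's own definitions. The size does not: 1% to 5% shown for a true 10% assumes a share of 10% to 50%.

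A reader might take the roughly 10% allowance in Section 11.1 as that share and conclude that rates are understated tenfold. The protocol does not support this. The allowance is a sample-size margin for early terminations and unevaluable patients, not a count of people with post-treatment time. Patients who fail the Week 52 eligibility check would add to that count, and those lost within 6 weeks of their last dose would reduce it.

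Treatment-emergent tables and all efficacy analyses are unaffected.

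**What to change.** Add a sentence to Section 11.4.3.1: for post-treatment adverse events, the denominator is the number of safety-population patients in each treatment group with at least 1 day of follow-up beyond the end of the on-treatment period, and that number is shown in the column header. Keep the safety population as denominator for treatment-emergent events.

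The cost is that sentence and one table shell. No data collection changes. The post-treatment percentages will rest on fewer patients and be less precise. They will also describe a group selected after randomization, so differences between arms in these tables should be read as descriptive.
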